### New Lesion Time Point Response (TPR)

---

Yes	Lesion present at follow-up visit either for the very first time or re-appearing (ie, lesion was present at baseline, disappeared at a follow-up visit and re-appeared later). Note: The appearance of one or more new lesions on CT or MRI scan is considered progression if these findings are unequivocally not due to a change in the imaging technique or modality. On bone scan, new lesions are not sufficient to qualify as PD. Confirmation should be obtained by performing CT or MRI of the area of concern to confirm results of bone scan. Preferred method for confirmation is MRI.
No	No new lesions present at follow-up.
Unable to Evaluate (UE)	Subject not assessed or incompletely assessed for new lesions.

---

CONFIDENTIAL

Protocol XL184-313 Protocol Amendment 3.0  
Page 178 of 193

---

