## TIME POINT RESPONSE CRITERIA

Target Lesion Time Point Response (TPR)	
Complete Response (CR)	Disappearance of all target lesions. All pathological lymph nodes (whether target or non-target) must have reduction in short axis to < 10 mm.
Partial Response (PR)	At least a 30% decrease in SoD of target lesions, taking as a reference the baseline SoD.
Stable Disease (SD)	Neither sufficient shrinkage to qualify for PR nor sufficient increase to qualify for PD.
Progressive Disease (PD)	At least a 20% increase in the SoD of target lesions, taking as a reference the smallest (nadir) SoD since (and including) baseline. In addition to the relative increase of 20%, the SoD must also demonstrate an absolute increase of at least 5 mm.
Not Applicable (NA)	No target lesion identified at baseline.
Unable to Evaluate (UE)	One or more target lesions are not imaged and the remainder of the SoD compared with the nadir SoD does not meet the criterion for PD.

SoD, baseline sum of diameters (longest for non-nodal lesions; short axis for nodal lesions).

If the target lesion for a subject meet the criteria for both PR and PD at a given time point, the target lesion response is PD.

If the nadir of SoD is 0 (ie, the subject had a prior target lesion CR), the reappearance of any prior target lesion to any degree constitutes PD.

Non-Target Lesion Time Point Response (TPR)	
Complete Response (CR)	Disappearance of all non-target lesions. All lymph nodes must be non-pathological in size (<10 mm short axis).
Non-CR / Non-PD	Persistence of one or more non-target lesion(s).
Progressive Disease (PD)	Unequivocal progression of non-target lesions. Unequivocal progression should normally not trump target lesion status. It must be representative of overall disease status change, not a single lesion increase.
Not Applicable (NA)	No non-target lesions identified at screening.
Unable to Evaluate (UE)	One or more non-target lesions are not imaged and the remaining non-target lesions do not meet the criterion for PD.

CONFIDENTIAL

Protocol XL184-313 Protocol Amendment 3.0  
Page 177 of 193

---

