### Evaluation of Overall Time Point Response

Target Lesion TPR	Non-target lesion TPR	New lesion TPR	Overall TPR
CR	CR or NA	No	CR*
CR	Non-CR/non-PD	No	PR*
CR	UE	No	PR*
PR	Non-PD or NA or UE	No	PR*
SD	Non-PD or NA or UE	No	SD
UE	Any except PD	No	UE
PD	Any	No or Yes	PD
Any	PD	No or Yes	PD
Any	Any	Yes	PD**
NA	CR	No	CR*
NA	Non-CR/Non-PD	No	Non-CR/non-PD
NA	UE	No	UE

CR, complete response; PR, partial response; SD, stable disease; PD, progressive disease, UE, unable to evaluate; NA, not applicable (no such lesions at screening); Any, CR, PR, SD, PD, NA, or UE.

The overall response at a given time point does not depend upon the overall response assigned at any prior or subsequent time point (ie, confirmation requirement is not considered when assigning time point responses).

\* Subjects with an overall response of CR or PR must have a follow-up tumor assessment performed no less than 4 weeks after the criteria for response are first met (this may be performed at the next scheduled tumor assessment). However, the presence, absence, or status at this follow up assessment is not considered when assigning a time point response at prior time points.

\*\* If a lesion disappears and reappears at a subsequent time point it should continue to be measured. However, the subject's response at the point in time when the lesion reappears will depend upon the status of his/her other lesions. For example, if the subject's tumor had reached a CR status and the lesion reappeared, then the subject would be considered PD at the time of reappearance. In contrast, if the tumor status was a PR or SD and one lesion which had disappeared then reappears, its maximal diameter should be added to the sum of the remaining lesions for a calculated response.

Furthermore, in order to identify potential delayed immune-mediated tumor response, subjects with an overall response of PD per RECIST 1.1 who continue with study treatment because of evidence of clinical benefit as assessed by the Investigator should have a follow-up tumor assessment no later than the next scheduled tumor assessment. However, the presence, absence, or status at this follow up assessment is not considered when assigning a time point response at prior time points.

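### Protocol Appendix F is inconsistent on lesions that re-appear during PR or SD: its New Lesion table makes them progression, while its overall-response footnote adds them to the sum of diameters

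*Protocol*

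**What the plan says.** Protocol Section 5.7.6.1 sends the reader to Appendix F for response and PD. Section 9.2.2.1 makes BIRC-determined PD per RECIST 1.1 the progression event for primary PFS. Four parts of Appendix F bear on a lesion that vanishes and comes back.

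- **New Lesion Time Point Response.** A new lesion is scored Yes if it is present "either for the very first time or re-appearing"; the table explains the second case as a baseline lesion that vanished during follow-up and later came back. The note beside it adds: "The appearance of one or more new lesions on CT or MRI scan is considered progression", barring a change of imaging technique or modality. No condition on CR, PR or SD is attached.
- **Evaluation of Overall Time Point Response, table.** The row with any target status, any non-target status and new lesion Yes gives PD, marked with a double asterisk. Every PR and SD row requires new lesion No.
- **Footnote to that PD entry.** At re-appearance the response "will depend upon the status of his/her other lesions". The CR example is "if the subject's tumor had reached a CR status and the lesion reappeared, then the subject would be considered PD at the time of reappearance". For PR or SD, "its maximal diameter should be added to the sum of the remaining lesions for a calculated response".
- **Target lesion rules.** Under Time Point Assessments, the baseline target or non-target label is kept, a vanished target lesion is recorded as 0 mm, and the sum is recomputed at each assessment. Under Time Point Response Criteria, target PD needs a rise of at least 20% and at least 5 mm over nadir. Only when the nadir sum is 0 does the text say that "the reappearance of any prior target lesion to any degree constitutes PD".

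The SAP fixes the date assigned to progression (Section 7.1.4) but gives no rule for re-appearing lesions.

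**The concern.** A reader who applies the New Lesion table as written calls PD as soon as a baseline lesion returns. A reader who applies the footnote to the same scan in a subject in PR or SD adds a diameter and may keep the subject in PR or SD. The first reader records the PFS event earlier.

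The same choice affects Investigator-assessed PFS, and it affects ORR and duration of response because best response is counted only through the first PD (SAP Section 7.5.1).

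There is also a route from the Investigator to the primary analysis. If the Investigator calls PD and stops treatment on that basis, scans may cease. A BIRC applying the footnote could then have no later scan, and the subject would be censored at the last adequate assessment. SAP Section 7.1.6.2 already lists Investigator PD without BIRC PD as a source of potentially informative censoring.

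**Working it through.** The plan states no figure on this point, so there is nothing to reproduce. The check is whether the two texts can give different answers on one scan, and over what range. All lesion sizes below are assumed; the thresholds (20% and 5 mm over nadir for PD, 30% below baseline for PR) are from Appendix F.

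**Example 1, subject in PR.** Baseline sum 100 mm. Nadir 50 mm, with one 12 mm target lesion gone. It returns at 6 mm.
- Sum: 50 + 6 = 56 mm.
- Change from nadir: 56/50 = 1.12, so +12% and +6 mm. The 5 mm condition is met but the 20% condition is not, so there is no target PD.
- Change from baseline: 1 − 56/100 = 44% decrease, so PR continues under the footnote.
- Under the New Lesion table: new lesion Yes, so PD on that date.

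**Example 2, subject in PR, range of disagreement.** Baseline 40 + 30 + 20 = 90 mm. Nadir 30 + 25 + 0 = 55 mm (39% decrease). The third lesion returns at x mm.
- x = 6: 61/55 = 1.109, not PD by the footnote.
- x = 10: 65/55 = 1.182, not PD by the footnote.
- x = 11: 66/55 = 1.200, PD under both texts.

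**Example 3, subject in SD.** Baseline 40 + 30 + 12 = 82 mm. Nadir 38 + 30 + 0 = 68 mm (17% decrease).
- x = 13: 81/68 = 1.191, not PD by the footnote.
- x = 14: 82/68 = 1.206, PD under both texts.

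**Where the texts agree.** After CR, both give PD. If target lesions had all vanished but non-target disease persisted (overall PR), the nadir-0 rule makes the target response PD, so the overall response is PD under either text. In PR or SD with a sum at or above the threshold, both give PD.

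**Non-target lesions.** The footnote speaks of a lesion without saying target. Non-target lesions are generally not measured and are not part of the target sum, so adding a diameter is not a usable instruction for them. In PR or SD the New Lesion table would then be the only explicit rule.

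**Size of a date shift.** CAP imaging is every 8 weeks through Week 50 and every 12 weeks afterwards. If the footnote rule reaches PD at the next scheduled scan, the event moves by 8 × 7/30.4375 = 1.8 months or 12 × 7/30.4375 = 2.8 months. If it reaches PD later, the shift is larger. This is a shift for one affected subject, not a shift in median PFS.

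**The case against.** The best defence is that the footnote is an exception to the row it hangs on. Its marker sits on the PD entry of the new-lesion row, and it has work to do only if re-appearing lesions are first coded Yes. On that reading one codes Yes, reaches PD, and then applies the qualification. The surrounding text supports the footnote: target labels are maintained, the sum is recomputed at each visit, and automatic PD on re-appearance is stated only for a nadir of 0, a limit that would be unnecessary if every re-appearance were already PD. This stands, and it shows that the re-appearance wording in the New Lesion table is the outlier. It does not remove the conflict. That table has no exception or cross-reference, and no row of the overall table allows PR or SD with new lesion Yes.

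Three stronger readings are tempting, and the documents do not support them.

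- **That primary PFS was read under two progression rules.** Central reads follow the BIRC Charter (Protocol Section 12.3), which is not supplied and may settle the matter.
- **That the footnote allows PD only after CR.** CR is its example; in PR or SD the calculated response is still PD once the thresholds are met.
- **That Appendix F contradicts itself again where it says "The overall response at a given time point does not depend upon the overall response assigned at any prior or subsequent time point".** The parenthesis that follows limits that statement to the confirmation requirement.

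The Investigator route is also narrower than it may look. Scans may cease only if treatment is stopped upon PD. Subjects treated beyond PD continue to be imaged, and investigators are encouraged to defer the call when progression is in doubt.

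**Conclusion.** The inconsistency is real and bears on the definition of the primary event. The New Lesion table makes any re-appearing baseline lesion progression. The footnote, in line with the sum-of-diameters and nadir-0 rules, requires a calculated response in PR or SD.

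The effect is confined to a lesion that re-appears during PR or SD while the sum stays below the PD threshold. In the assumed cases that means a returning lesion of up to 10 mm (PR) or 13 mm (SD). For such a subject the PD date could move by about one scan interval or more. For non-target lesions in PR or SD the footnote offers no workable rule.

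The documents give no frequency, so no effect on the hazard ratio or on the comparison between arms can be derived, and none is claimed. The primary analysis is still triggered by 249 events; power and alpha are unaffected. The conclusion rests on the Appendix F text alone; the BIRC Charter could resolve the central read but is not stated to govern investigators.

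**What to change.** 1. In the New Lesion table, limit re-appearance to lesions that re-appear after CR, and cross-refer to the double-asterisk footnote. Do not delete the re-appearance wording outright: the nadir-0 rule covers target lesions only, so a non-target lesion returning after CR would no longer reach the new-lesion row.
2. State how a re-appearing non-target lesion is assessed when the subject is in PR or SD, since its diameter is not in the target sum.
3. Confirm that the BIRC Charter and the investigator instructions use the same rule. For any reads already done, document which rule was applied.

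The cost is an appendix wording change, a short memo to readers and investigators, and a charter check. No change to sample size, event targets or analysis methods is needed.

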### Evaluation of Overall Time Point Response

Target Lesion TPR	Non-target lesion TPR	New lesion TPR	Overall TPR
CR	CR or NA	No	CR*
CR	Non-CR/non-PD	No	PR*
CR	UE	No	PR*
PR	Non-PD or NA or UE	No	PR*
SD	Non-PD or NA or UE	No	SD
UE	Any except PD	No	UE
PD	Any	No or Yes	PD
Any	PD	No or Yes	PD
Any	Any	Yes	PD**
NA	CR	No	CR*
NA	Non-CR/Non-PD	No	Non-CR/non-PD
NA	UE	No	UE

CR, complete response; PR, partial response; SD, stable disease; PD, progressive disease, UE, unable to evaluate; NA, not applicable (no such lesions at screening); Any, CR, PR, SD, PD, NA, or UE.

The overall response at a given time point does not depend upon the overall response assigned at any prior or subsequent time point (ie, confirmation requirement is not considered when assigning time point responses).

\* Subjects with an overall response of CR or PR must have a follow-up tumor assessment performed no less than 4 weeks after the criteria for response are first met (this may be performed at the next scheduled tumor assessment). However, the presence, absence, or status at this follow up assessment is not considered when assigning a time point response at prior time points.

\*\* If a lesion disappears and reappears at a subsequent time point it should continue to be measured. However, the subject's response at the point in time when the lesion reappears will depend upon the status of his/her other lesions. For example, if the subject's tumor had reached a CR status and the lesion reappeared, then the subject would be considered PD at the time of reappearance. In contrast, if the tumor status was a PR or SD and one lesion which had disappeared then reappears, its maximal diameter should be added to the sum of the remaining lesions for a calculated response.

Furthermore, in order to identify potential delayed immune-mediated tumor response, subjects with an overall response of PD per RECIST 1.1 who continue with study treatment because of evidence of clinical benefit as assessed by the Investigator should have a follow-up tumor assessment no later than the next scheduled tumor assessment. However, the presence, absence, or status at this follow up assessment is not considered when assigning a time point response at prior time points.

## **Confirmation**

The main goal of confirmation of objective response is to avoid overestimating the response rate observed. For subjects with an overall response of PR or CR at a given time point, a follow-up tumor assessment must be performed no less than 4 weeks after the criteria for response are first met. This may be performed at the next scheduled tumor assessment.

In order to identify potential delayed immune-mediated tumor response, subjects with an overall response of PD per RECIST 1.1 who continue with study treatment because of evidence of clinical benefit as assessed by the Investigator should have a follow-up tumor assessment no later than the next scheduled tumor assessment. However, the presence, absence, or status at these follow up assessments is not considered when assigning a time point response at prior time points.

## **Best Overall Response**

Best overall response, incorporating confirmation requirements, will be derived during statistical analysis from the series of time point responses and need not be considered when assigning response at each time point.

CONFIDENTIAL

Protocol XL184-313 Protocol Amendment 3.0  
Page 180 of 193

## Appendix G: List of Strong Inducers and Inhibitors of CYP3A4

Cabozantinib is a CYP3A4 substrate (Section 7.3.1 Potential drug interactions with cabozantinib).

Chronic co-administration of cabozantinib with drugs known to be strong inducers of the CYP3A4 family may decrease cabozantinib concentrations and therefore should be avoided during treatment with cabozantinib. St. John's Wort (*Hypericum perforatum*) is also known to be an inducer of CYP3A4 and should be avoided.

Co-administration of cabozantinib with strong inhibitors of the CYP3A4 family may increase cabozantinib concentrations and should be avoided during treatment with cabozantinib. Grapefruit, star fruit and Seville oranges may also increase plasma concentrations of cabozantinib and should be avoided during treatment with cabozantinib.

Strong Inhibitors of CYP3A4	Strong Inducers of CYPA4
Antivirals Boceprevir Cobicistat Conivaptan Danoprevir Dasabuvir Elvitegravir Indinavir Lopinavir Nelfinavir Ombitasvir Paritaprevir Ritonavir Saqueinavir Telaprevir Tipranavir  Anti-Fungals Itraconazole Ketoconazole Posaconazole Voriconazole  Antibiotics Clarithromycin Telithromycin Troleandomycin  Conivaptan Diltiazem Grapefruit juice/star fruit/Seville oranges Idelalisib Nefazodone	Carbamazepine Efavirenz Enzalutamide Erythromycin Mitotane Modafinil Nevirapine Oxcarbazepine Phenytoin Rifampin St. John's Wort

CONFIDENTIAL

Protocol XL184-313 Protocol Amendment 3.0  
Page 181 of 193

This table is not all-inclusive. Please refer to the FDA website for the most updated lists of substrates, inducers, and inhibitors of selected CYP450 isozyme pathways:

<http://www.fda.gov/Drugs/DevelopmentApprovalProcess/DevelopmentResources/DrugInteractionsLabeling/ucm080499.htm>

CONFIDENTIAL

Protocol XL184-313 Protocol Amendment 3.0  
Page 182 of 193

## **Appendix H: Collection, Follow-Up, and Documentation Requirements for AEs, AESIs, and SAEs**

All AEs that are not serious and not AESIs (AEs of special interest; see [Table 8-1](#)) that start or worsen after the first dose of study treatment through the 30-day post-treatment follow-up (FU-1) visit are to be entered into the electronic CRF data capture system (EDC). Such events continuing at the FU-1 visit are to be documented as “ongoing” in the EDC and do not require further documentation for study purposes. These events do not require a Drug Safety SAE Form to be completed.

Additional requirements apply to the following events:

- All SAEs that are judged by the investigator to be not related to study treatment that start or worsen after the subject’s initial informed consent through the 100-day post-treatment follow-up (FU-2) visit are to have a Drug Safety SAE Form completed. Such events continuing at the FU-2 visit are to be documented as “ongoing” in the EDC and do not require further documentation for study purposes.
- All AEs leading to study treatment discontinuation that are judged by the Investigator to be related to study treatment and that are continuing at the FU-2 visit are to be followed by the Investigator until resolution, defined as fully resolved or  $\leq$  Grade 2 severity or the event is deemed stable/irreversible by the Investigator. In the EDC, only documentation of the status of “ongoing” at the FU-2 visit is required. If serious, the requirements for related SAEs apply.
- All AESIs (regardless of seriousness) that start or worsen after the subject’s initial informed consent through the FU-2 visit are to have a Drug Safety SAE Form completed and be entered into the EDC. Such events continuing at the FU-2 visit are to be followed until resolution (as defined above), with evidence of resolution provided on updates to the Drug Safety SAE Form. In the EDC, only documentation of the status of “ongoing” at the FU-2 visit is required.
- All SAEs that are judged by the Investigator to be related to study treatment that start or worsen at any time after the subject’s initial informed consent are to have a Drug Safety SAE Form completed. Such events that occur prior to the FU-2 visit are to be entered into the EDC. Such events continuing at the FU-2 visit are to be followed until resolution (as defined above), with evidence of resolution provided on updates to the Drug Safety SAE Form. In the EDC, only documentation of the status of “ongoing” at the FU-2 visit is required.

CONFIDENTIAL

A summary of the event surveillance (Table H-1) and follow-up requirements (Table H-2) are shown in the following page:

CONFIDENTIAL

Protocol XL184-313 Protocol Amendment 3.0  
Page 184 of 193

**Table H-1: Requirements for Documenting the Incidence of AEs, SAEs, and AESIs:**

Event type	Event surveillance period (inclusive):			
	EDC CRF a		Drug Safety SAE Form	
	Period start	Period stop	Period start	Period stop
AE: nonserious, non-AESI	first dose	FU-1	NA	NA
SAE: not related	IC	FU-2	IC	FU-2
Related AE leading to study treatment discontinuation	first dose	EOT date	NA (if nonserious)	NA (if nonserious)
AESI: nonserious (AESIs: irAEs, potential DILI, Other; Table 8-1 )	IC	FU-2	IC	FU-2
Related SAE	IC	FU-2	IC	ever

AE, adverse event; AESI, adverse event of special interest ([Table 8-1](#)); EDC, electronic CRF data capture system; CRF, case report form; DILI, drug-induced liver injury; EOT date, end of treatment date (later of the date of decision to discontinue study treatment or date of last dose); FU-1, follow-up visit 30 days after EOT date; FU-2, follow-up visit 100 days after EOT date; IC, informed consent; irAE, immune-related AE; NA, not applicable; SAE, serious AE.

a See CRF completion guidelines for instructions regarding the appropriate page(s) to be completed

**Table H-2: Requirements for Following up on Events Documented and Reported in Table H-1:**

Event type	If ongoing at...	...follow until...	Event follow-up requirements		
			...and document following on:		
			Source documents	EDC CRF	Drug Safety SAE Form
AE: nonserious, non-AESI	FU-1	NA	status at FU-1	status at FU-1	NA
SAE: not related, non-AESI	FU-2	NA	status at FU-2	status at FU-2	status at FU-2
Related AE leading to study treatment discontinuation	FU-2	Resolution b	evidence of resolution	status at FU-2	NA (if nonserious)
AESI: regardless of seriousness (AESIs: irAEs, potential DILI, Other; Table 8-1 )	FU-2	Resolution b	evidence of resolution	status at FU-2	evidence of resolution
Related SAE	FU-2	Resolution b	evidence of resolution	status at FU-2	evidence of resolution

AE, adverse event; AESI, adverse event of special interest ([Table 8-1](#)); EDC, electronic CRF data capture system; CRF, case report form; DILI, drug-induced liver injury; EOT date, end of treatment date (later of the date of decision to discontinue study treatment or date of last dose); FU-1, follow-up visit 30 days after EOT date; FU-2, follow-up visit 100 days after EOT date; IC, informed consent; irAE, immune-related AE; NA, not applicable; SAE, serious AE.

a See CRF completion guidelines for instructions regarding the appropriate page(s) to be completed

b Defined as: AE is fully resolved or  $\leq$  Grade 2 severity or the event is deemed stable/irreversible by the Investigator

CONFIDENTIAL

